| Monthly Contacts | Approximately every 25 – 35 days from birth through Visit 4-NB. | | May occur more often between Birth and Visit 2-NB at the discretion of study personnel. Should coincide with Monthly post-delivery contacts described in Table 1 and Table 2 . Contacts are additional to and do not replace protocol specified Visits. |
| Birth → C1-NB | 270 days | 256 – 286 days | |
| Birth → V5-NB | 365 days | 330 - 400 days | |

V= Visit;NB=Newborn

CONFIDENTIAL209544 (RSV MAT-004)
Protocol Amendment 3 Final**2. INTRODUCTION****2.1. Study Rationale**

GSK Biologicals is developing an investigational Respiratory Syncytial Virus (RSV) vaccine for administration to pregnant women, with the aim of preventing RSV-associated lower respiratory tract illnesses (LRTIs) in their infants by transfer of maternal antibodies. The vaccine candidate is based on a recombinant RSV F protein, engineered to preferentially maintain the pre-fusion conformation (RSVPreF3).

A Phase I/II study of this candidate vaccine is underway (study RSV MAT-001; NCT 03674177). In this study, healthy non-pregnant women received a single intramuscular (IM) dose of either 30, 60 or 120 µg of the candidate vaccine, or saline placebo. The GSK Biologicals iSRC responsible for monitoring the safety data in RSV MAT-001 and the Independent Data Monitoring Committee (IDMC) who will oversee safety monitoring in RSV-MAT-004 will review the unblinded safety data from all subjects, (i.e. ~375 active vaccine and ~125 saline placebo recipients) up to 90 days post vaccination. The current study will only be initiated after a favorable evaluation of all available safety data from completed/ ongoing non-clinical studies and from the ongoing RSV MAT-001 clinical study.

In the current (RSV MAT-004) study, a single IM dose of the candidate vaccine will be administered for the first time to pregnant women in the third trimester. Two dose levels were selected for evaluation; the selection criteria are described in Section 4.3. Subjects will be vaccinated year-round and will not be limited to seasonal enrollment.

Safety, reactogenicity and immunogenicity of the candidate vaccine (at 2 dose levels) will be evaluated in maternal subjects for up to 6 months after delivery; safety evaluation will include assessment of pregnancy outcomes and pregnancy-related and neonatal adverse events of special interest (AESIs). The study will also evaluate the transfer of RSV-specific antibodies from vaccinated maternal subjects to the infants, the incidence of medically attended RSV-associated respiratory tract illnesses (MA-RTI) in maternal subjects, the incidence of RSV-associated respiratory tract / lower respiratory tract illnesses (RTI/LRTI) in infants for up to 6 months after delivery/birth, and the incidence of medically attended and serious adverse events for up to 12 months, in infants born to vaccinated mothers.

2.2. Background

Please refer to the current Investigator's Brochure (IB) for background information on RSV infection, the rationale for the maternal immunization approach described in this protocol, information regarding the pre-clinical and clinical studies of the RSV Maternal (RSVPreF3) vaccine.

2.3. Benefit/Risk assessment

Detailed information about the known and expected benefits and risks and reasonably expected adverse events of the RSV Maternal (RSVPreF3) vaccine can be found in the IB.

CONFIDENTIAL209544 (RSV MAT-004)
Protocol Amendment 3 Final

The balance of anticipated benefits and apparent risks associated with the RSV maternal (RSVPreF3) vaccine continues to be acceptable following ongoing systematic review of the safety data.

3. OBJECTIVE(S) AND ENDPOINT(S)**Table 5 Study objectives and endpoints**

| Primary Safety objectives | Primary Safety endpoint(s) |
|--|--|
| To evaluate the safety and reactogenicity of a single IM dose of study vaccine administered to maternal subjects, from Visit 1 up to 6 weeks after delivery | Occurrence of solicited administration site and systemic events) during a 7-day follow-up period after vaccination (i.e. the day of vaccination and 6 subsequent days). |
| | Occurrence of any hematological (complete blood count with differential and platelet count) or biochemical (alanine amino-transferase, aspartate amino-transferase, creatinine, blood urea nitrogen) laboratory abnormality at baseline (up to 15 days before vaccination) and Day 8 (Visit 2) |
| | Occurrence of unsolicited AEs that occur during a 30-day follow-up period after vaccination (i.e. the day of vaccination and 29 subsequent days). |
| | Occurrence of serious adverse events (SAEs), AEs leading to study withdrawal, and medically attended AEs (MAEs) from Visit 1 (Day 1) up to 6 weeks after delivery (Day 43 post-delivery, Visit 6). |
| To evaluate pregnancy outcomes and pregnancy-related AESIs after a single IM dose of study vaccine administered to maternal subjects, from Visit 1 up to 6 weeks after delivery (Visit 6). | Pregnancy outcomes from Day 1 (Visit 1) up to 6 weeks after delivery (Day 43 post-delivery, Visit 6). These include live birth with no congenital anomalies, live birth with congenital anomalies, fetal death/still birth (antepartum or intrapartum) with no congenital anomalies, fetal death/still birth (antepartum or intrapartum) with congenital anomalies, elective/therapeutic termination with no congenital anomalies and elective/therapeutic termination with congenital anomalies. |
| | Pregnancy-related AESIs from Day 1 (Visit 1) up to 6 weeks after delivery (Day 43 post-delivery, Visit 6). These include but are not limited to maternal death, hypertensive disorders of pregnancy (gestational hypertension, pre-eclampsia, pre-eclampsia with severe features including eclampsia), antenatal bleeding (morbidly adherent placenta, placental abruption, cesarean scar pregnancy, uterine rupture), postpartum hemorrhage, fetal growth restriction, gestational diabetes mellitus, non-reassuring fetal status, pathways to preterm birth (premature preterm rupture of membranes, preterm labor, provider-initiated preterm birth), chorioamnionitis, oligohydramnios, polyhydramnios, gestational liver disease (intrahepatic cholestasis of pregnancy, acute fatty liver of pregnancy), maternal sepsis.* |
| To evaluate the safety of the study vaccine, including neonatal AEs of special interest, in infants born to maternal subjects who were vaccinated with a single IM dose of study vaccine, up to 6 weeks after birth. | The occurrence of neonatal AEs of special interest (reported up to 6 weeks after birth). These include but are not limited to small for gestational age, low birth weight including very low birth weight, neonatal encephalopathy, congenital microcephaly (postnatally or prenatally diagnosed), congenital anomalies (major external structural defects, internal structural defects, functional defects), neonatal death (in a preterm live birth or in a term live birth), neonatal infections (blood stream infections, meningitis, respiratory infection), respiratory distress in the neonate, preterm birth, failure to thrive, large for gestational age, macrosomia.* |
| | Occurrence of SAEs, AEs leading to study withdrawal and MAEs from birth up to 6 weeks after birth. |

CONFIDENTIAL209544 (RSV MAT-004)
Protocol Amendment 3 Final

| Primary Immunogenicity objectives | Primary Immunogenicity endpoints |
|--|---|
| To evaluate the immunogenicity of a single IM dose of study vaccine in maternal subjects at Day 31 and at Delivery. | RSVPreF3 IgG-specific antibody concentration, and Neutralizing antibody titers against RSV-A Measured on blood samples collected from vaccinated maternal subjects at Day 1 before vaccination (Visit 1), Day 31 (Visit 3), and at Delivery (Visit 5). |
| To evaluate RSV-specific antibody levels in infants born to maternal subjects who were vaccinated with a single IM dose of study vaccine at birth | RSVPreF3 IgG-specific antibody concentration, and Neutralizing antibody titers against RSV-A. Measured on the cord blood sample collected at delivery, or on a blood sample collected from the infant within 3 days after birth (if no cord blood sample can be obtained). |
| To evaluate the transfer of RSV-specific antibodies from maternal subjects vaccinated with a single IM dose of study vaccine to their infants at the time of delivery. | The ratio between cord blood* and maternal RSVPreF3 IgG-specific antibody concentrations *or an infant blood sample collected within 3 days after birth (if no cord blood sample can be obtained). |
| Secondary Safety objectives | Secondary Safety endpoints |
| To evaluate the safety of a single IM dose of study vaccine in maternal subjects, up to 6 months after delivery | From Day 1 (Visit 1) through 6 months after delivery (Visit 8), occurrences of SAEs, MAEs, and AEs leading to study withdrawal. |
| To evaluate the safety of the vaccine in infants born to maternal subjects who were vaccinated with a single IM dose of study vaccine, up to 1 year of age | From birth through 6 months (Visit 4-NB) after birth, occurrences of SAEs, AEs leading to study withdrawal, and MAEs From birth through 1 year (Visit 5-NB) after birth, occurrences of SAEs, AEs leading to study withdrawal, and MAEs. |
| To estimate the incidence of RSV-associated, medically attended RTIs (MA-RTIs) in maternal subjects vaccinated with a single IM dose of study vaccine, from vaccination up to 6 months post-delivery (Visit 8). | Occurrence of RSV-associated MA-RTIs (RSV-MA-RTIs) up to 6 months post-delivery (Visit 8) |
| To estimate the incidence of RSV-associated lower respiratory tract illness (LRTI), severe LRTI and very severe LRTI and RSV-associated hospitalization in infants born to maternal subjects who were vaccinated with a single IM dose of study vaccine, from birth up to 6 months of age. | From birth to 6 months (Visit 4-NB), occurrences of RSV-associated LRTI(s), Severe LRTI(s), very severe LRTIs and RSV-associated hospitalizations (according to the case definitions). |
| Secondary immunogenicity objectives | Secondary Immunogenicity endpoints |
| To evaluate the immunogenicity of a single IM dose of study vaccine in maternal subjects in terms of RSVPreF3 IgG-specific antibody concentrations and neutralizing antibodies against RSV-A at Day 43 after Delivery (Visit 6). | RSVPreF3 IgG-specific antibody concentration Neutralizing antibody titers against RSV-A Measured on the blood sample collected at Day 43 post-delivery (Visit 6). |
| To evaluate the immunogenicity of a single IM dose of study vaccine in maternal subjects in terms of RSV-B neutralizing antibodies at Day 1 before vaccination (Visit 1), Day 31 (Visit 3), at Delivery (Visit 5) and at Day 43 post-delivery (Visit 6). | Neutralizing antibody titers against RSV-B Measured on blood samples collected from vaccinated maternal subjects at Day 1 before vaccination (Visit 1), Day 31 (Visit 3), at Delivery (Visit 5) and at Day 43 post-delivery (Visit 6). |

CONFIDENTIAL209544 (RSV MAT-004)
Protocol Amendment 3 Final

| Secondary immunogenicity objectives | Secondary Immunogenicity endpoints |
|--|---|
| To evaluate RSV-specific antibodies in infants born to maternal subjects who were vaccinated with a single IM dose of study vaccine, up to 6 months after birth. | RSVPreF3 IgG-specific antibody concentration Neutralising antibody titres against RSV-A Neutralising antibody titres against RSV-B For neutralizing antibody titers against RSV-B only: measured on the cord blood sample collected at delivery, or on a blood sample collected from the infant within 3 days after birth (if no cord blood sample can be obtained). (Note: RSV-A neutralizing antibody at birth is a primary immunogenicity objective). For all 3 RSV-specific antibody assessments: measured in a subcohort of infants at Day 43 after birth (sub-cohort V2-NB), in a subcohort of infants at Day 121 (sub-cohort V3-NB) after birth and in a subcohort of infants at D181 after birth (sub-cohort V4-NB). Each infant will be randomly assigned to 1 of these 3 cohorts at the time of maternal randomization to treatment study intervention. |
| Tertiary objectives: To further evaluate the humoral response to the RSV maternal vaccine, which may include RSVpreF3 specific IgG subclasses, antibodies competing for binding to specific RSVpreF3 epitopes, and other exploratory endpoints. To evaluate the presence of other respiratory viruses in nasal swabs collected from maternal subjects and their infants (via an Allplex Respiratory Viruses Panel or alternative, performed for RSV A/B-positive samples and if deemed necessary for RSV A/B-negative samples.) | |

[figure not shown]
*Maternal and neonatal AESI and pregnancy outcomes should be recorded in the eCRF along with GAIA assessment and level of diagnostic certainty when applicable. Of note, some adverse events of special interest fall under a single category but have multiple subcategories. For example, hypertensive disorders of pregnancy is an event with three subcategories that include: 1) gestational hypertension; 2) pre-eclampsia; and 3) pre-eclampsia with severe features (including eclampsia). For each event, the investigator should identify the event and select the applicable sub-category.”

4. STUDY DESIGN

4.1. Overall design

Figure 1 and Figure 2 provide overviews of the study design for maternal and infant subjects, respectively. Section 1.3 provides Schedules of Activities (SoAs) for maternal and infant subjects. Section 9.5.1 describes the sequence of analyses for maternal and infant subject data.

CONFIDENTIAL

[figure not shown]
209544 (RSV MAT-004)
Protocol Amendment 3 Final**Figure 1 Overall design – maternal subjects**

H/B= hematology/biochemistry, Hct- hematocrit; I= humoral immune response

If Screening blood sample collected ≤ 15 days before Visit 1, hematology/biochemistry not required at Visit 1

Subjects will be vaccinated year-round and will not be limited to seasonal enrolment

*Pregnancy-related AESIs identified after Day 43 will continue to be reported as such.

Figure 2 Overall design– infant subjectsNB = Newborn; I=humoral immune response: infants will be randomized 1:1:1 to **one** of the 3 subcohorts shown.*Blood sample to be collected within 3 days after birth **ONLY** if a cord blood sample is not collected

**Neonatal AESIs identified after Day 43 (e.g., congenital anomalies) will continue to be reported as such.

***Infant subjects' parent(s)/LAR(s) will be contacted at least monthly to ensure RTI eDiary compliance.

Safety and disease surveillance data collected *after* Visit 4-NB will be reported in the database *in Epoch 003*.

CONFIDENTIAL209544 (RSV MAT-004)
Protocol Amendment 3 Final

- Study Type: self-contained.
- Experimental design: Phase II, observer-blind, randomised, placebo controlled, multi-centric, multi-country study with 3 parallel groups.
- Study Duration: Approximately 9 months (including the screening visit) for participating pregnant women; approximately 1 year after birth for participating infants.
- Control: Placebo.
- Epochs 001, 002 and 003 begin and end as described in [Table 6](#).
- Blinding is as described in [Table 6](#).
- Randomized intervention allocation is described in Section [6.2](#).
- Study (intervention) groups are described in [Table 6](#).

CONFIDENTIAL

209544 (RSV MAT-004)
Protocol Amendment 3 Final**Table 6 Study groups, subcohorts, interventions, epochs and blinding foreseen in the study (Amended 30-SEP-2020)**

| Study groups (Maternal subjects, allocated 1:1:1) | Approximate Number of maternal subjects | Age of maternal subject at enrolment (Min/Max) | Intervention name | Blood sample subcohorts (infant subjects, allocated 1:1:1 within each maternal study group) | Approximate Number of infant subjects | Study groups for randomization (Allocation 1:1:1:1:1:1:1:1) | Epochs (Blinding) | | |
|---|---|--|-------------------|---|---------------------------------------|---|--|--|--|
| | | | | | | | Epoch 001 Maternal subjects Only (Screening) | Epoch 002 Maternal subjects V1-V8 Infant subjects V1-NB – V4NB (observer-blind)* | Epoch 003 Infant subjects only Contact 1-NB – V5-NB (single-blind) |
| RSV MAT 60 | Up to 100 | 18 – 40 years | RSVPreF3_60 | BS1_60 | Up to 33 | RSVMAT60_BS1 | • | • | • |
| | | | | BS2_60 | Up to 33 | RSVMAT60_BS2 | | • | |
| | | | | BS3_60 | Up to 33 | RSVMAT60_BS3 | | • | |
| RSV MAT 120 | Up to 100 | 18 – 40 years | RSVPreF3_120 | BS1_120 | Up to 33 | RSVMAT120_BS1 | • | • | • |
| | | | | BS2_120 | Up to 33 | RSVMAT120_BS2 | | • | |
| | | | | BS3_120 | Up to 33 | RSVMAT120_BS3 | | • | |
| Control | Up to 100 | 18 – 40 years | Control | BS1_C | Up to 33 | Control_BS1 | • | • | • |
| | | | | BS2_C | Up to 33 | Control_BS2 | | • | |
| | | | | BS3_C | Up to 33 | Control_BS3 | | • | |

M=maternal subject; I=infant; Control = Placebo; Blood sampling subcohorts are abbreviated “BS1;” “BS2;” “BS3” and correspond to visits 2-NB (Day 43), 3-NB (Day 121) and 4-NB (Day 181), respectively.

* After the second analysis, the study will not be considered observer blind as the investigator brochure will be updated to include safety information presented by treatment group. This could lead to inadvertent unblinding of investigators and site staff to some subjects’ treatment assignments. The subjects themselves will remain blinded throughout their participation in the study.

- Data collection: standardized Electronic Case Report Form (eCRF). Electronic diaries (e-diaries) for solicited event data, and notifications regarding occurrence of unsolicited events (including medically attended events and SAEs), and symptoms of respiratory tract illnesses in infant subjects.
- Safety monitoring: Refer to section 8.2.3 for detailed description of holding rules and safety monitoring.

CONFIDENTIAL209544 (RSV MAT-004)
Protocol Amendment 3 Final**4.2. Scientific rationale for study design****4.2.1. Study population**

The study population mirrors that of the intended indication: healthy women in the third trimester of pregnancy.

4.2.2. Rationale for the use of placebo

The placebo group serves as a control for safety, reactogenicity, and immunogenicity assessments.

4.2.3. Safety considerations

As this is the first time the RSV maternal (RSVPreF3) vaccine will be administered to pregnant women, enrolment will be limited to 10 subjects per day across all sites until the first 30 subjects have been dosed. Within any given study site, these subjects will be vaccinated sequentially and at least 60 minutes apart.

In addition, throughout the study:

- All subjects will be required to remain at the site for 60 minutes following vaccination, and
- The data will be reviewed by a safety review team (SRT) and by an independent data monitoring committee (IDMC), and
- Holding rules will be applied.

The risk of Enhanced Respiratory Disease related to boosting pre-existing maternal antibody and transfer of vaccine-induced neutralizing antibodies from mother to infant is considered negligible. However, as data evaluating this risk are expected before vaccinating larger numbers of pregnant women, surveillance and evaluation (Section 8.4) of all RTIs in infants and medically attended-RTIs in mothers through 6 months post-delivery has been implemented.

4.2.4. Sub-cohorts for blood sampling in infants

Sub-cohorts for blood sampling have been defined to limit discomfort and risk to infants while ensuring enough observations to support robust evaluation of immune response (see [Figure 4](#) and [Table 6](#)).

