The timing of an event-driven site visit (e.g., to further evaluate a potential AE or MA-RTIs) cannot be defined with precision in the protocol. Event-driven visits may occur throughout the study. **Note:** • is used to indicate a study procedure that requires documentation in the individual eCRF. ○ is used to indicate a study procedure that does not require documentation in the individual eCRF. V = visit; D = day; GA = gestational age; MA-RTI = medically attended respiratory tract illness; PD = post delivery; Hct = hematocrit.

CONFIDENTIAL209544 (RSV MAT-004)
Protocol Amendment 3 Final**Table 2 Intervals between study visits – maternal subjects**

| Interval | Optimal interval | Allowed interval | Additional Information |
|------------------|----------------------------------|--------------------------------------|---|
| Screening → V1 | 4 days | 1– 28 days | The screening interval extends from Day -28 to Day -1 (the day before dosing). If a subject is screened but not vaccinated within the allowed interval, a re-screening can be done to establish the subject's eligibility. Please make sure the subject's gestational age is still within the allowed range, refer to Section 10.7 for guidance on gestational age assessment. |
| V1 → V2 | 7 days | 7 – 14 days | |
| V1 → V3 | 30 days | 20 - 45 days | |
| V1 → V4 | 60 days | 50–75 days | |
| V5 (delivery) | 0 days | 1 day before to 3 days post delivery | Collect maternal blood sample at any point from the day before up to delivery. If blood is not collected during delivery, collect maternal blood sample no later than 3 days after delivery. A cord blood sample should be collected at the time of each delivery. If cord blood cannot be collected at delivery, a blood sample should be collected from the infant subject as soon as possible and no later than 3 days after birth. |
| V5 → V6 | 42 days | 40 – 60 days | |
| V5 → V7 | 120 days | 110 -140 days | Visit may coincide with infant subject's routine vaccination visit if consistent with the participating country's routine infant vaccination schedule) |
| V5 → V8 | 180 days | 165 – 200 days | |
| Monthly contacts | Approximately every 25 – 35 days | | Monthly until Visit 8. May occur more often between Visit 5 and Visit 6 at the discretion of study personnel. Contacts are additional to and do not replace protocol specified Visits. |

V=Visit

CONFIDENTIAL

209544 (RSV MAT-004)
Protocol Amendment 3 Final**Table 3 Schedule of activities for infants**

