| Epochs | Epoch 002 | | | | | | Epoch 003 | | Additional Information |
|---|-----------|---|----------|----------|------------------|---------------------|-----------|-----------|--|
| | | To coincide with maternal visits 6, 7, 8 | | | | Event-Driven | | | |
| Visit / Contact | V1-NB | V2-NB | V3-NB | V4-NB | Monthly contacts | RTI Visit | C1-NB | V5-NB | NB=Newborn Monthly Contacts coincide with maternal monthly contacts. RTI Visit: Sections 8.4.3 and 8.4.5. |
| Age of infant | | 6 weeks | 4 months | 6 months | | | 9 months | 12 months | |
| Visit Day | Birth | D43 | D121 | D181 | | | D271 | D365 | Table 4 |
| Check Inclusion / exclusion criteria | • | | | | | | | | Sections 5.1.2 , 5.2.2 |
| Re-consent if required by local regulations | • | | | | | | | | |
| Record infant subject study number | • | | | | | | | | |
| Record subcohort for immunogenicity blood sampling | • | | | | | | | | Section 6.3.3 |
| Distribute infant's subject card | 0 | | | | | | | | Section 8.3.4 |
| Demographic data and lifestyle characteristics | • | • | • | • | | | • | • | Section 8.2.2.1 , Record at Visit 1-NB and if changes in lifestyle characteristics thereafter |
| Apgar score | • | | | | | | | | At 1, 5 and 10 minutes, if available |
| Weight, length, head circumference, physical examination | • | • | • | • | | | | • | Section 8.2.2.2 |
| Blood sample if no cord blood ~2.5 ml | • | | | | | | | | Adjust volume if weight ≤ 2.5 Kg. Refer to Table 12 . |
| Blood sample (immunology, infants) ~2.5 ml | | • | • | • | | | | | 1 sample at one of these visits, as per infant's assigned subcohort. Adjust volume if weight ≤ 2.5 Kg. Refer to Table 12 |
| Concomitant medications / vaccinations | • | • | • | • | • | • | • | • | Sections 6.5.2 , 6.5.3 |
| Neonatal AESIs | • | • | | | | | | | Sections 8.3.3 , 10.3.8 . Must submit an Expedited AE Report |
| Suspected, probable and confirmed cases of COVID-19 infection | • | • | • | • | • | • | • | • | |

CONFIDENTIAL

209544 (RSV MAT-004)
Protocol Amendment 3 Final

| Epochs | Epoch 002 | | | | | | Epoch 003 | | Additional Information |
|--|-----------|---|----------|----------|------------------|---------------------|-----------|-----------|--|
| | | To coincide with maternal visits 6, 7, 8 | | | | Event-Driven | | | |

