6.3.2. Randomisation to study intervention

Up to 300 eligible pregnant women will be randomly assigned to 3 study (intervention) groups in a 1:1:1 ratio and at the same time, their (as yet unborn) infants will be randomly assigned to 3 blood sampling subcohorts (also in a 1:1:1 ratio). This yields up to 100 pregnant women per group and up to 33 infants per blood sampling subcohort within each group, for an overall allocation of 1:1:1:1:1:1:1:1. Refer to [Table 6](#), [Figure 3](#) and [Figure 4](#).

CONFIDENTIAL209544 (RSV MAT-004)
Protocol Amendment 3 Final**Figure 3 Allocation of maternal subjects to study (intervention) groups**

*Numbers are approximate and represent maximum subject enrolment.

Figure 4 Allocation of infant subjects to blood sampling subcohorts

*Numbers are approximate and represent maximum subject enrolment.

The randomisation of supplies within blocks will be performed at GSK, using MATERIAL EXcellence (MatEx), a program developed for use in Statistical Analysis System (SAS) (Cary, NC, USA) by GSK. Entire blocks will be shipped to the study centres/warehouse(s).

To allow GSK to take advantage of greater rates of recruitment in this multi-centre study and to thus reduce the overall study recruitment period, an over-randomisation of supplies will be prepared.

CONFIDENTIAL209544 (RSV MAT-004)
Protocol Amendment 3 Final**6.3.3. Intervention allocation to the subjects**

Upon providing the maternal subject identification number, an automated internet based system (SBIR) will allocate the maternal subject to an intervention number and her (as yet unborn) infant subject to a blood sampling subcohort. The system's randomisation algorithm will use a minimisation procedure accounting for maternal age at the time of vaccination (≥ 18 and < 35 years of age or ≥ 35 years of age), gestational age at the time of vaccination ($28^{0/7}$ - $31^{0/7}$; $31^{1/7}$ - $33^{6/7}$) and center. Minimisation factors will have equal weight in the minimisation algorithm.

When the automated Internet-based system (SBIR) is not available, please refer to the SBIR user guide or SPM for specific instructions.

Refer to the SPM for additional information about intervention number allocation.

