| Infant subjects | 
 • RSVPreF3 IgG-specific antibody concentration • Neutralising antibody titres against RSV-A • Neutralising antibody titres against RSV-B 
For all 3 RSV-specific antibody assessments: measured in a subcohort of infants at Day 43 after birth (sub-cohort V2-NB), in a subcohort of infants at Day 121 (sub-cohort V3-NB) after birth and in a subcohort of infants at D181 after birth (sub-cohort V4-NB). Each infant will
 | 
For each assay, at each timepoint and by study group
 
 • Antibody titres/concentrations will be displayed using reverse cumulative curves. • GMTs/ GMCs will be tabulated with 95% CI and represented graphically. 
In addition, analyses will include exploratory evaluation of the persistence of RSV specific antibodies in infants through time, and half-life analysis modelling of logarithm transformed RSV antibody concentrations/titers over time.
 
Between group evaluation on vaccine formulations in terms of RSVPreF3 IgG-specific antibody concentrations / neutralizing antibody titers will be performed on cord blood at Delivery, and on blood samples collected at 6 weeks, 3-4 months and 6 months post-birth using a mixed effect model on the
 |

CONFIDENTIAL209544 (RSV MAT-004)
Protocol Amendment 3 Final

| | Secondary Immunogenicity Endpoints | Statistical Analysis Methods |
|--|--|---|

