| | 
be randomly assigned to 1 of these 3 cohorts at the time of maternal randomization to intervention
 
For neutralizing antibody titers against RSV-B only: measured on the cord blood sample collected at delivery, or on a blood sample collected from the infant within 3 days after birth (if no cord blood sample can be obtained). (Note: RSV-A neutralizing antibody at birth is a primary immunogenicity objective).
 | 
logarithm₁₀ transformation of the concentrations/titers, including the pre-vaccination logarithm₁₀ transformation of the concentrations/titers from maternal subjects, the vaccine groups, gestational age at vaccination, gestational age at birth (> 37 weeks ; ≤ 37 weeks), and the interval between vaccination and delivery as covariates if appropriate and needed.
 
In addition, if cord blood samples are missing in 20% or more of infants in a single study group, and if the data permit: RSV antibody concentrations/titers and persistence of RSV antibody concentrations/titers in infants through time will be evaluated separately in infants with cord blood samples and in infants from whom, instead, a blood sample was obtained within 3 days after birth.
 
The relationship between RSVPreF3 IgG-specific antibody concentration and RSV-A neutralizing antibody, between RSV-A neutralizing antibody and RSV-B neutralizing antibody, and between RSV-B neutralizing antibody and RSVPreF3 IgG-specific antibody concentration at delivery will be explored using scatter plots of individual values.
 |

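### Infant antibody estimates at Days 43, 121 and 181 each rest on one random third of a group; a joint model with the birth titres already collected would make them more precise

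*Protocol*

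**What the plan says.** **Sampling.** Table 2 (Section 1.3) asks for a birth titre from everyone: "A cord blood sample should be collected at the time of each delivery". An infant sample within 3 days of birth is the fallback. For later visits, Table 3 gives each infant "1 sample at one of these visits, as per infant's assigned subcohort". Table 5 (Section 3) makes the split random: "Each infant will be randomly assigned to 1 of these 3 cohorts at the time of maternal randomization to treatment study intervention". Section 6.3.2 gives the numbers: "This yields up to 100 pregnant women per group and up to 33 infants per blood sampling subcohort within each group".

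**Rationale.** Section 4.2.4 says the split limits discomfort and risk "while ensuring enough observations to support robust evaluation of immune response". The protocol gives no infant precision or power figure behind this. Its only titre-based power table, Table 25 in Section 9.2.2, concerns mothers at Day 31.

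**Analysis.** For infants, Section 9.4.4.2 plans reverse cumulative curves and GMTs/GMCs with 95% CI "For each assay, at each timepoint and by study group". It adds exploratory persistence and half-life modelling over time. It also plans a between-group evaluation, by a mixed effect model on log10 values, for cord blood and the three later samples. The terms listed are the mother's pre-vaccination titre, vaccine group, gestational age at vaccination and at birth, "and the interval between vaccination and delivery as covariates if appropriate and needed". Whether the timepoints are fitted together or one at a time is not stated.

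**The concern.** Subcohort membership is randomised, so a Day 121 value that is absent because the infant was assigned to Day 43 or Day 181 is missing completely at random. Each such infant should still have a birth titre. Infant antibody after maternal vaccination is passively acquired, so the birth titre plausibly predicts what remains later. Birth titres from all infants in a group therefore carry information about that group's mean at every later visit.

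The per-visit GMTs/GMCs cannot use this information. The between-group model, as its terms are listed, does not use it either: nothing ties an infant's birth value to its later value. Section 9.4.3.2 describes a mixed effect model in nearly the same words for cord blood alone, with one value per infant, so the word mixed does not in itself imply a joint fit.

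At stake is how sharply the trial describes the persistence of infant antibody under each dose. More precision is available without another infant blood draw, which fits the stated aim of sparing infants.

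**Working it through.** **1. The plan's own figure.** Table 25 uses a one-sided 5% two-sample t-test. With δ = log10(fold ratio), the noncentrality is δ / (SD × √(2/n)) on 2n − 2 degrees of freedom. For SD 0.3 and a 1.4-fold ratio, δ = 0.146:
- n = 45: 0.146 / 0.0632 = 2.31, power 74.1% (Table 25: 74.1%).
- n = 90: 0.146 / 0.0447 = 3.27, power 94.6% (Table 25: 94.6%).

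Eight rows were checked; all agree within 0.1 percentage point.

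**2. Infants per later visit.** Allocation: 300 / 9 = 33.3 per subcohort per group. Section 9.2.2 assumes 10% non-evaluable; if that also holds for infants (an assumption), 270 / 9 = 30 with a later titre and 90 per group with a birth titre.

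**3. Precision on the subcohort alone.** No infant SD is given, so the maternal values in Table 25 are borrowed for illustration. Section 9.4.6.2 expects more variability in cord blood than at Day 31, so they may be optimistic.
- 95% CI factor for one GMT at SD 0.4: 10^(t × 0.4/√n). For n = 30, 10^(2.045 × 0.0730) = 1.41. For n = 90, 10^(1.987 × 0.0422) = 1.21.
- Power for a 1.5-fold dose ratio at n = 30 per group: 51.6% at SD 0.4 and 72.6% at SD 0.3.

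**4. Gain from a joint fit.** Let n = 30 infants have the later titre, N = 90 the birth titre, and r be the correlation between them on the log10 scale. The variance of the later group mean becomes, in units of SD²,

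(1 − r²)/n + r²/N, against 1/n for the visit alone.

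The ratio is 1 − r²(1 − n/N) = 1 − (2/3)r². The standard error falls by 1 − √ratio, and the effective n is 30/ratio. The protocol does not give r; the range below is assumed. The last two columns put the effective n into the power formula of step 1.

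| r | Variance ratio | Simulated ratio | SE reduction | Effective n | CI factor, SD 0.4 | Power 1.5-fold, SD 0.4 | Power 1.5-fold, SD 0.3 |
|---|---|---|---|---|---|---|---|
| 0 (visit only) | 1.000 | 1.03 | 0% | 30 | 1.41 | 51.6% | 72.6% |
| 0.3 | 0.940 | 0.96 | 3% | 32 | 1.40 | 54% | 75% |
| 0.5 | 0.833 | 0.86 | 9% | 36 | 1.37 | 58% | 79% |
| 0.7 | 0.673 | 0.69 | 18% | 45 | 1.33 | 66% | 87% |
| 0.8 | 0.573 | 0.58 | 24% | 52 | 1.30 | 72% | 91% |
| 0.9 | 0.460 | 0.46 | 32% | 65 | 1.26 | 80% | 95% |

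The simulated column is the regression estimator over 20,000 runs with 30 of 90 infants. It runs slightly above the formula at low r, because the slope must itself be estimated; at r = 0 this costs about 3% in variance.

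**5. Which r applies.** The planned model already allows adjustment for the mother's baseline titre, gestational ages and interval to delivery. For group ratios from that model, r is therefore the partial correlation after those terms, which may be smaller than the raw one.

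**The case against.** The strongest reply is that the protocol is not wrong here. Randomised subcohorts make per-visit GMTs unbiased, and tabulating them is standard. Section 9.1 makes all analyses descriptive, and no power is claimed for infants. Section 9.4.1 leaves technical detail and missing data to the SAP, and a joint fit with an infant random effect would already use every birth titre. The gain also rests on a correlation nobody has stated. All of this stands, and it limits the point to efficiency.

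Four stronger readings are tempting, and the document supports none of them:
- *That the other infants' cord titres are thrown away.* They feed the primary cord-blood GMTs/GMCs, the between-group cord model and, for IgG, the placental transfer ratio (Section 9.4.3.2). They are unused only for the later-visit estimates.
- *That separate fits per visit are fixed.* A joint fit is unstated, not excluded.
- *That dose selection is undermined.* Section 9.4.6.2 draws on the totality of data but focuses on cord titres and names Day 31 and delivery, not the later visits.
- *That Section 4.2.4 makes a false claim.* It is a design rationale and sets no precision target.

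A practical objection also stands. Random assignment covers subcohort membership, not per-protocol membership. The exclusion windows for immune-modifying drugs and blood products run to the assigned visit (Section 9.3.3.1.2), and confirmed RSV infection during the analysis interval may exclude an infant (Section 9.3.3.1.3). Birth titres from infants screened over shorter windows cannot enter a Day 181 per-protocol mean without a stated rule.

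**Conclusion.** The point holds as an improvement to the estimator, not as an error. The Day 43, 121 and 181 GMTs/GMCs each rest on about 30 infants per group. The between-group model as listed does not use the birth titres of the remaining 60 or so for those visits. Nothing is biased.

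The gain is negligible to modest at a partial correlation of 0.3 to 0.5, and worth having at 0.7 to 0.9, where a visit gains the equivalent of about 15 to 35 infants per group. These figures assume 30 of 90 infants evaluable, a roughly linear relation on the log10 scale and, for power, maternal SDs applied to infants. Missing birth samples would reduce the gain.

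**What to change.** In Section 9.4.4.2, state that the infant between-group model is fitted jointly to the log10 cord/birth titre of all infants and each infant's assigned later titre. It should have group-by-visit means, the covariates already listed and within-infant covariance. A two-outcome model for each later visit is enough, because no infant has two later samples. Report model-based GMTs/GMCs and group ratios with 95% CI beside the raw subcohort GMTs/GMCs.

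Two cautions belong in the same text:
- Do not enter the cord titre as a plain covariate in a subcohort model. It is measured after vaccination and carries the dose effect, so conditioning on it would remove part of what is being estimated.
- State which infants' birth titres enter the per-protocol version, given exclusion windows that depend on subcohort.

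The cost is a few sentences, one more model per assay, that eligibility rule, and reliance on an approximately linear birth-to-later relation on the log10 scale. No extra samples or subjects are needed.
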